2.7.1.1 ASAS40 response

Response at Week 12 [REDACTED] to ASAS40 will be analyzed analogously to the primary endpoint (see [Section 2.5.1](#) for definition of the ASAS40 responder).

2.7.1.2 ASAS20 response

Response at Week 12, Week 24 [REDACTED] to ASAS20 will be will be analyzed analogous to the primary endpoint (see [Section 2.5.1](#) for definition of the ASAS20 responder).

2.7.1.3 ASAS partial remission

The proportion of patients meeting the ASAS definition for PR at Week 12, Week 24 [REDACTED] will be analyzed by means of a multiple logistic regression model including treatment and center as factors and weight as covariate (see [Section 2.5.1](#) for definition of the ASAS PR responder).

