12.5.1 Analysis of secondary [REDACTED] efficacy endpoints

ASAS20/40 response

ASAS20/ ASAS40 response at Week 12, Week 24 [REDACTED] will be evaluated using the multiple logistic regression model utilized for the primary efficacy variable.

ASAS partial remission

The proportion of patients meeting the ASAS definition for PR at Week 12, Week 24 [REDACTED] will be analyzed by means of a multiple logistic regression model including treatment and center as factors and weight as covariate.

AS disease activity score

The proportion of patients meeting the ASDAS definition of inactive disease (< 1.3), ASDAS clinically important improvement (change in ASDAS ≥ 1.1) and ASDAS major improvement (change in ASDAS ≥ 2.0) as well as ASDAS low disease activity (< 2.1) at Week 12, Week 24 [REDACTED] will be evaluated using a multiple logistic regression model with treatment group and center as factors and weight and Baseline ASDAS as covariates.

Furthermore, the between-treatment difference in change from Baseline in ASDAS will be evaluated using a mixed-effect model repeated measures (MMRM). Treatment group and analysis visit as factors and Baseline ASDAS index score and weight as continuous covariates

will be included in the model. Treatment group by analysis visit and Baseline ASDAS index score by analysis visit will be included as interaction terms in the model. An unstructured covariance matrix will be assumed. The treatment effect for the secukinumab T2T regimen at different analysis visits will be determined from the pairwise comparison performed between the 2 treatment groups.

Bath ankylosing spondylitis disease activity index

The proportion of patients achieving the BASDAI50 response criteria at Week 12, Week 24 [REDACTED] will be analyzed by means of a multiple logistic regression model with treatment and center as factors and weight and Baseline BASDAI as covariates.

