2.5.2 Statistical hypothesis, model, and method of analysis

The null hypothesis to be rejected is that the odds of ASAS40 response at Week 24 are equal in both treatment groups. The corresponding alternative hypothesis is that the odds of response at Week 24 are higher under the secukinumab T2T approach compared to a SOC regimen.

Let p_j denote the proportion of ASAS40 responders at 24 weeks for treatment group j , $j=0,1$ where

0 corresponds to the SOC regimen

1 corresponds to the secukinumab T2T regimen

The following hypotheses will be tested:

$H_0: (p_1 / 1-p_1) / (p_0 / 1-p_0) = 1$ vs. $H_A: (p_1 / 1-p_1) / (p_0 / 1-p_0) \neq 1$

In other words:

H_A : The odds ratio (OR) of achieving an ASAS40 response at Week 24 for the comparison of secukinumab T2T vs. SOC is different from 1.

The **primary analysis** will be performed comparing treatments with respect to the primary efficacy variable in a multiple logistic regression model with treatment and center as factors and weight as well as Baseline CRP level as covariates. The adjusted OR, the corresponding 95% confidence interval (CI) and the p-value will be given. The H_0 of equal odds will be rejected if the 2-sided p-value from the logistic regression model for the factor “treatment” is < 0.05 ; however, superiority of secukinumab T2T approach will be claimed only if the direction is correct, i.e. if the odds of response are larger under secukinumab T2T approach.

Tables will also show the number and percentage of patients achieving ASAS40 response.

The primary efficacy analysis will be based on the FAS. The primary analysis will be performed when all subjects have completed the Week 24 assessment.

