2.7.2 Statistical hypothesis, model, and method of analysis

Between-treatment comparisons for binary variables in the FAS population (e.g. ASAS20, ASAS40) at individual analysis visits will be evaluated using a logistic regression model with treatment and center as factors and weight as covariates. Odds ratios and 95% CI will be presented for appropriate treatment comparisons. Continuous variables will be evaluated, using a MMRM, with treatment group and analysis visit as factors and Baseline score for related assessment and weight as continuous covariates. Treatment group by analysis visit and Baseline related assessment by analysis visit will be included as interaction terms in the model. An unstructured covariance matrix will be assumed. If covariance matrix will not converge then other covariance structure will be used like compound symmetry, autoregressive structure etc. The treatment effect for the secukinumab T2T regimen at different analysis visits will be determined from the pairwise comparison performed between the 2 treatment groups. The adjusted least square means, point estimate of difference between treatment means, 95% CI for treatment difference and p-value will be presented.

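### SAP 2.7.2 gives ASAS20 and ASAS40 a weight-only model that contradicts the endpoint-specific models, and ASAS partial remission is modelled without any baseline disease covariate

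*SAP*

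**What the plan says.** **Primary endpoint.** SAP 2.5.2 analyses ASAS40 at Week 24 in a "multiple logistic regression model with treatment and center as factors and weight as well as Baseline CRP level as covariates". Protocol 12.4.2 specifies the same model.

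**ASAS20 and ASAS40 as secondary endpoints.** Protocol 12.5.1 says these "will be evaluated using the multiple logistic regression model utilized for the primary efficacy variable". SAP 2.7.1.1 says that response "to ASAS40 will be analyzed analogously to the primary endpoint", and SAP 2.7.1.2 says that ASAS20 is "analyzed analogous to the primary endpoint". All three bring in Baseline CRP.

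**General rule for binary endpoints.** SAP 2.7.2 gives ASAS20 and ASAS40 as its examples and says that such comparisons "will be evaluated using a logistic regression model with treatment and center as factors and weight as covariates". CRP is absent.

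**ASAS partial remission.** SAP 2.7.1.3 specifies a logistic model "including treatment and center as factors and weight as covariate". Protocol 12.5.1 has the same model.

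**Other responder endpoints.** BASDAI50 adjusts for Baseline BASDAI (SAP 2.7.1.5), the ASDAS responses for Baseline ASDAS (SAP 2.7.1.6) and the SF-36 response for its baseline score (SAP 2.7.1.13).

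**Code and declared changes.** The only logistic code, in SAP 5.6.1, has a CRP term. SAP Section 4 declares no change to the protocol's analyses.

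**The concern.** Two separate things look wrong.

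First, a programmer who follows 2.7.1 and one who follows 2.7.2 would fit different models to the same endpoint. The odds ratio is non-collapsible: adding a prognostic covariate changes the quantity estimated as well as its standard error. The two models can therefore report different odds ratios, intervals and p-values. In an open-label trial it is better not to leave that choice until the data are in hand.

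Second, partial remission means a score below 2 in all four core ASAS domains (SAP 2.5.1). It is a state reached, not a change from baseline, so where a patient starts should bear on whether the patient gets there. The closest relatives, ASDAS < 1.3 and < 2.1, are also absolute thresholds and do adjust for the starting level. Neither document explains why partial remission is treated differently. At stake is some power on a demanding secondary endpoint.

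**Working it through.** **1. Covariates beyond treatment and center, side by side**

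| Endpoint | Endpoint-specific section | SAP 2.7.2 |
|---|---|---|
| ASAS40, Week 24 (primary) | weight, Baseline CRP (2.5.2) | outside its scope |
| ASAS40, Week 12 | weight, Baseline CRP (2.7.1.1) | weight |
| ASAS20, Weeks 12 and 24 | weight, Baseline CRP (2.7.1.2) | weight |
| Partial remission | weight (2.7.1.3) | weight |
| BASDAI50 | weight, Baseline BASDAI (2.7.1.5) | weight |
| ASDAS responses | weight, Baseline ASDAS (2.7.1.6) | weight |
| SF-36 response | weight, baseline score (2.7.1.13) | weight |

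Read as a general rule, 2.7.2 agrees with the endpoint-specific section only for partial remission. The SAS template, with its CRP term, matches neither 2.7.2 nor the partial remission model.

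**2. The plan's own sample size**

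Inputs from SAP Section 3: 50% v 30%, two-sided 0.05, power 90%, continuity-corrected chi-square.

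- n = [1.960·√(2·0.4·0.6) + 1.2816·√(0.5·0.5 + 0.3·0.7)]² / 0.2² = 124.
- With continuity correction: (124/4)·[1 + √(1 + 4/(124·0.2))]² = 133.8, so 134 per arm, as stated.
- Odds ratio: (0.5/0.5)/(0.3/0.7) = 2.33, as stated (2.3).

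The covariate question does not touch this calculation.

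**3. What omitting a baseline covariate costs**

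The documents do not say how strongly any baseline measure predicts response, so this was varied. The model was logit P(response) = α(arm) + b·x, with x standard normal and α(arm) chosen to hold the marginal rates fixed. There were 6,000 simulated trials of 150 v 150 per cell, fitted with and without x, with a two-sided Wald test at 0.05. Center and weight were left out.

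Only 50% v 30% comes from the plan. The other rates are assumptions. Protocol Table 4-1 reports partial remission at Week 16 in an earlier trial of 9.5% on 150 mg and 21.1% on 300 mg, but no standard-of-care rate is given.

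Power (%), without → with the covariate, by assumed odds ratio per SD:

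| Rates | 1.25 | 1.5 | 2 | 3 |
|---|---|---|---|---|
| 50% v 30% | 94.3→94.2 | 94.5→95.2 | 94.4→95.7 | 95.1→97.9 |
| 44% v 30% | 71.9→72.4 | 71.3→72.9 | 70.4→74.5 | 71.4→79.3 |
| 20% v 10% | 68.2→68.0 | 67.8→68.8 | 68.9→71.0 | 68.0→74.4 |
| 15% v 8% | 47.0→47.4 | 46.2→47.2 | 47.2→49.5 | 46.0→50.9 |

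The last two rows are the partial-remission-type cases. The gain is −0.2 to 2.3 points up to an odds ratio per SD of 2, and 4.9 to 6.4 points at 3. The simulation error of one entry near 68% is about √(0.68·0.32/6000) = 0.6 points.

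**4. Where the gain comes from**

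At 50% v 30% with an odds ratio of 2 per SD, median values were:

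- Without x: log OR 0.846 (OR 2.33), SE 0.242, ratio 3.50.
- With x: log OR 0.941 (OR 2.56), SE 0.257, ratio 3.66.

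Adjustment makes the standard error larger. Power rises because the conditional odds ratio moves further from 1. The same pair shows what two models for one endpoint can report: 2.33 from one and 2.56 from the other.

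**The case against.** **The partial remission model is a choice, not a mistake.** It is the same in the protocol and the SAP and it is unambiguous. This stands: a reader might infer that the SAP departs from the protocol here, and it does not. Adding a covariate is an improvement, and it would itself be the departure.

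**The rest of the plan points to CRP for ASAS20 and ASAS40.** The endpoint-specific sections, the SAS template and the empty Section 4 all agree against 2.7.2. This also stands, and it makes the repair easy. It does not remove the conflict, because 2.7.2 names these two endpoints. Nothing suggests that the sponsor means to choose between models after seeing results.

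**The primary analysis is safe.** A reader who sees ASAS40 named in 2.7.2 might infer that the primary test also has two models. It does not: SAP 2.5.2 and Protocol 12.4.2 fix it, and 2.7.2 sits under the secondary objectives. SAP 2.6 lists no key secondary objectives, so no confirmatory claim hangs on the affected endpoints.

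**Precision is not lost.** A reader used to linear models might infer that leaving out a baseline covariate widens the standard error. In logistic regression it does the reverse, as the working shows.

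**Sparse data may matter more.** At an assumed 20% v 10% there would be 30 + 15 = 45 partial remissions, and at 15% v 8% about 22.5 + 12 = 34.5, spread over center effects whose number is not stated. That is a fair caution against adding terms freely. It argues for one covariate only and for a check on the center factor. It does not explain why this endpoint alone has no baseline measure.

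**Conclusion.** The point holds in two parts, both minor.

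The wording conflict is certain. ASAS40 at Week 12 and ASAS20 at Weeks 12 and 24 each have two specified models, and 2.7.2 also contradicts the BASDAI50, ASDAS and SF-36 responder models. The size of any resulting difference depends on how prognostic Baseline CRP is, which the documents do not say.

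The missing baseline covariate for partial remission costs some power: about 0 to 6 points over the rates and prognostic strengths tried, and no more than about 2 points unless the odds ratio per SD exceeds 2. This rests on assumed response rates, one normal covariate, and models without center or weight. Neither part affects the primary analysis or the sample size.

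**What to change.** 1. Rewrite SAP 2.7.2 so that binary endpoints use the models in their own sections, stating that ASAS20 and ASAS40 use the primary model with Baseline CRP. Give endpoint-specific logistic code in SAP 5.6.1, or mark the CRP term there as applying only to ASAS20 and ASAS40.
2. Add one pre-specified covariate, Baseline ASDAS, to the partial remission model, in the same form as in the ASDAS responder models. It is preferable to a mean of the four ASAS domains because the back pain domain may be total or nocturnal pain, so that mean is not uniquely defined. Entry requires an ASDAS of at least 2.1 at Baseline, so the score should be available for every eligible patient. Record the addition in SAP Section 4 as a change from Protocol 12.5.1.

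The first change is wording and code only and restores the protocol's model. The second needs no new data, but it is a declared departure from the protocol and adds a parameter to a model with few events. If the sponsor prefers to keep the protocol's partial remission model, one sentence giving the reason would do.

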2.7.1.4 Bath ankylosing spondylitis disease activity index (BASDAI)

The BASDAI consists of a 0 through 10 scale (0 being no problem and 10 being the worst problem, captured as a continuous VAS), which is used to answer 6 questions pertaining to the 5 major symptoms of AS:

1. Fatigue
2. Spinal pain
3. Joint pain/swelling
4. Areas of localized tenderness (called enthesitis, or inflammation of tendons and ligaments)
5. Morning stiffness severity
6. Morning stiffness duration

To give each symptom equal weighting, the mean (average) of the two scores relating to morning stiffness is taken and is then added to the sum of the first 4 questions. The resulting 0 to 50 score is divided by 5 to give a final 0 – 10 BASDAI score. BASDAI is a quick and simple index taking between 30 seconds and 2 minutes to complete. At least 4 questions should be non-missing to calculate the BASDAI score ([Haywood et al 2002](#)). Otherwise, BASDAI score will be missing. If Q5 and/or Q6 are missing or one of Q1 to Q4 is missing the total sum should be divided by 4 instead of 5. If two of Q1 to Q4 is missing and both Q5 and Q6 are not missing the sum should be divided by 3.

The BASDAI will be summarized descriptively (total score, change from Baseline) by treatment group and overall, at Week 12, Week 24 [REDACTED] for FAS. The between-treatment difference in change from Baseline in BASDAI will be also evaluated using a MMRM. Treatment group and analysis visit as factors and Baseline BASDAI score and weight as continuous covariates will be included in the model. Treatment group by analysis visit and Baseline BASDAI score by analysis visit will be included as interaction terms in the model. An unstructured covariance matrix will be assumed. The treatment effect for the secukinumab T2T regimen at different analysis visits will be determined from the pairwise comparison performed between the 2 treatment groups.

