2.7.1.12 ASAS health index

The ASAS-HI is a disease-specific questionnaire that was developed based on the comprehensive International Classification of Functioning, Disability and Health Core Set (also known as the ICF Core Set) for AS ([Kiltz et al 2014](#)). The ASAS HI is a linear composite measure and contains 17 items (dichotomous response option: “I agree” and “I do not agree”), which cover most of the international classification of functioning (ICF) Core Set. The ASAS HI contains items addressing categories of pain, emotional functions, sleep, sexual function, mobility, self-care, and community life. The total sum of the ASAS HI ranges from 0 to 17, with a lower score indicating a better health status.

A total score can be analyzed if no more than 20% of the data (i.e. 3 items) are missing. The total score is calculated as follows for respondents with one to a maximum of three missing responses: Total score = $(x / 17-m)*17$, where x=item summation score and m number of missing items. Cases with more than three missing responses cannot be allocated a total score.

In addition, the Environmental Factor (EF) Item Set contains items addressing categories of support/relationships, attitudes and health services. The EF Item Set contains 9 dichotomous items with an identical response option but without a sum score because of its multidimensional nature ([Kiltz et al 2014](#)).

The ASAS-HI will be summarized descriptively (total score, change from Baseline) by treatment group and overall at Week 12, Week 24 [REDACTED] for FAS. The between-treatment difference in change from Baseline in ASAS-HI will be evaluated using a MMRM. Treatment group and analysis visit as factors and Baseline ASAS-HI score and weight as continuous covariates will be included in the model. Treatment group by analysis visit and Baseline ASAS-HI score by analysis visit will be included as interaction terms in the model. An unstructured

covariance matrix will be assumed. The treatment effect for the secukinumab T2T regimen at different analysis visits will be determined from the pairwise comparison performed between the 2 treatment groups.

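### The SAP's BASDAI rule for incomplete forms uses a divisor that does not always match the number of components summed, so some scorable forms are off by 25% (wrong as written, minor)

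*SAP*

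**What the plan says.** For a complete BASDAI form, SAP 2.7.1.4 states that "the mean (average) of the two scores relating to morning stiffness is taken and is then added to the sum of the first 4 questions", and then: "The resulting 0 to 50 score is divided by 5 to give a final 0 – 10 BASDAI score". The score is therefore the mean of five components.

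For incomplete forms, the same section has three rules:
- the minimum: "At least 4 questions should be non-missing to calculate the BASDAI score";
- divisor 4: "If Q5 and/or Q6 are missing or one of Q1 to Q4 is missing the total sum should be divided by 4", in place of 5;
- divisor 3: "If two of Q1 to Q4 is missing and both Q5 and Q6 are not missing the sum should be divided by 3".

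The section does not say whether a single answered stiffness item stays in the sum. It has no separate divisor for a form that lacks one stiffness item and one of Q1 to Q4.

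For ASAS-HI with one to three missing items, SAP 2.7.1.12 prints the total as (x / 17-m) × 17, "where x=item summation score and m number of missing items". It gives the range as: "The total sum of the ASAS HI ranges from 0 to 17, with a lower score indicating a better health status".

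The protocol has no missing-item rule for either instrument (Protocol 8.3.1.4, Appendix 5 and 8.5.1.3), so in these documents the SAP is the only authority.

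**The concern.** A prorated mean keeps its scale only if the divisor is the number of components in the numerator. The BASDAI rule fixes the divisor by which items are missing and leaves the numerator undefined when exactly one stiffness item is answered. Two programmers following the text could produce different scores for the same form, and neither of the two natural choices is right for every form.

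BASDAI change and BASDAI50 at Weeks 12 and 24 are listed secondary endpoints (SAP Table 2-2). A mis-scored form can change a patient's BASDAI50 status. Non-responder imputation (SAP 2.7.3) does not catch this, because the form counts as scored and not as missing.

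The ASAS-HI formula, taken literally, subtracts m after dividing by 17 and so leaves the stated scale.

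**Working it through.** **Inputs** (all from SAP 2.7.1.4): five components; complete-data divisor 5; at least 4 of 6 items answered; divisors 4 and 3 as quoted above.

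**Complete data.** With every item at 10: (10 + 10 + 10 + 10 + 10) / 5 = 10. This reproduces the stated 0–10 range.

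**Incomplete data.** There are 1 + 6 + 15 = 22 response patterns with none, one or two items missing, all of them scorable. With every answered item at 10, a correct score is 10.

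| Missing | Patterns | Divisor | Lone stiffness item dropped | Lone stiffness item kept |
|---|---|---|---|---|
| None | 1 | 5 | 50/5 = 10 | 50/5 = 10 |
| One of Q1–Q4 | 4 | 4 | 40/4 = 10 | 40/4 = 10 |
| Only Q5 or only Q6 | 2 | 4 | 40/4 = 10 | **50/4 = 12.5** |
| Both Q5 and Q6 | 1 | 4 | 40/4 = 10 | 40/4 = 10 |
| Two of Q1–Q4 | 6 | 3 | 30/3 = 10 | 30/3 = 10 |
| One of Q5/Q6 and one of Q1–Q4 | 8 | 4 | **30/4 = 7.5** | 40/4 = 10 |

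If the lone item is dropped, 8 of 22 patterns are wrong, each by −25%. If it is kept, 2 of 22 are wrong, each by +25%. No pattern is wrong under both. A third and less natural reading halves the lone item. It gives 45/4 = 11.25 in the third row and 35/4 = 8.75 in the last, which is ±12.5%.

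With all answered items at 6, dropping gives 3 × 6 / 4 = 4.5 and keeping gives 5 × 6 / 4 = 7.5, where 6 is correct.

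**Effect on BASDAI50**, taking response as an improvement of at least 50% and a complete baseline score of 6:
- Dropped: Q1 and Q6 missing, all answers 4. The score is 3 × 4 / 4 = 3.0, an apparent improvement of 50%. The correct score is 4.0, an improvement of (6 − 4)/6 = 33%. This is a false responder.
- Kept: Q6 missing, all answers 3. The score is 5 × 3 / 4 = 3.75, an apparent improvement of 37.5%. The correct score is 3.0, an improvement of 50%. A true responder is lost.

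**ASAS-HI.** Read literally, (x/17 − m) × 17 = x − 17m. Over all possible x this runs from −17 to −1 for m = 1, −34 to −19 for m = 2 and −51 to −37 for m = 3. With x = 8 and m = 2 it gives −26. With the bracket, 8/15 × 17 = 9.07, and the range is 0 to 17 for every m.

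**After the fix.** With the divisor set to the number of components summed, all 22 BASDAI patterns return 10 under either treatment of the lone stiffness item.

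**The case against.** The best defence of the BASDAI rule is that it treats one missing stiffness item and two missing stiffness items alike. That makes sense only if the component is dropped whenever either is missing. On that reading, losing stiffness alone, one of Q1 to Q4 alone, or two of Q1 to Q4 is scored correctly in every case. The 12.5 maximum then does not arise. The remaining combination could be called unaddressed rather than wrongly scored. SAP section 1 also places further programming specifications in a separate document, and the scoring paragraph cites a published source; neither can be seen here.

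Most of this stands. Dropping is the more natural reading, and the values above 10 belong to the less natural one. But the divisor-4 sentence, read as it is written, does cover the remaining combination, and the four-answer minimum requires that form to be scored. If the combination is unaddressed instead, the SAP still gives no correct divisor for it.

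A reader might infer that the ASAS-HI endpoint will be reported with negative totals. The documents do not support that. The 0–17 range is stated beside the formula, SAP 2.5.2 writes odds just as loosely (p1 / 1-p1), and the literal formula is negative for every possible x, so it could hardly pass unnoticed. It is a missing bracket.

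A reader might also infer a bias in the treatment comparison or in the primary result. The documents do not support that either:
- ASAS40 uses the stiffness items directly and not the BASDAI total (SAP 2.5.1).
- ASDAS is not calculated if any component is missing (SAP 2.7.1.6).
- Sites must check forms for completeness and prompt for unanswered items (Protocol 8.5.1 and Appendix 7).
- Nothing suggests that missing items would differ by arm.

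The same appendix does let a site accept an unfinished form, so the patterns are possible, though probably uncommon.

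**Conclusion.** Wrong as written, but minor. No natural reading of the BASDAI rule is correct for all scorable forms. The error is −25% when one stiffness item and one of Q1 to Q4 are missing (stiffness component dropped, the more natural reading), or +25% when only one stiffness item is missing (lone item kept). The faulty pattern and the sign depend on the reading.

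The reach is BASDAI change and BASDAI50. The ASAS-HI formula is an editorial slip that matters only if programmed literally. The number of affected records is probably small, but this is a judgement: the documents give no item-missing rate, and no effect on a treatment comparison has been shown. The conclusion assumes that the SAP text is followed; the separate programming specifications may already be right.

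**What to change.** In SAP 2.7.1.4, replace the two divisor sentences with a rule that does two things:
- states whether a single answered stiffness item represents the stiffness component or the component is dropped;
- divides the sum by the number of components actually summed (5, 4 or 3), given at least four answered items.

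Either choice for the lone item works arithmetically, and the sponsor should follow the convention of its scoring source. The SAP already prorates cleanly for ASQoL (2.7.1.14) and FACIT-Fatigue (2.7.1.15), so this brings BASDAI into line.

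In SAP 2.7.1.12, write Total = x / (17 − m) × 17.

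The cost is one rewritten rule and one bracket, plus a check that the programming specifications agree. Design, data collection, sample size and the primary analysis do not change.
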